### **5.4. Pre-Induction**

#### **5.4.1. Group Assigned to Outpatient Cervical Ripening**

After Dilapan-S® placement, subject will be monitored for at least 30 minutes. If no contraindications, such as tachysystole, active vaginal bleeding, rupture of membranes or nonreassuring fetal testing (defined as minimal or absent variability, abnormal baseline, or presence of decelerations) evidence of labor, or other serious medical conditions deemed by the clinical staff or the attending physician to preclude outpatient cervical ripening develop after insertion, the subjects will be randomized. After randomization subject will record the pain she experienced during insertion in the patient's survey (see Appendix 3). Those subjects randomized to outpatient ripening will be given the option to either stay in a hotel or, if they are able to reach the hospital within 60 minutes, return home. The cost for the hotel will be covered by the study budget. Subjects at CUMC will solely be given the option to stay at home. Subjects will be allowed to ambulate, shower and perform regular activity during that period. "Nothing per vagina" will be allowed (incl. intercourse, tampons etc.). Subjects will also be instructed to return to L&D unit 12 hours after insertion, or earlier if any excessive bleeding, rupture of membranes, pain or other concerns (contractions, decreased fetal movement) develop before the 12 hours. Special leaflet (Appendix 2) will be provided to subjects leaving the hospital, with detailed instruction, emergency contacts to appropriate study/clinical staff and space to document of oral medication taken for pain relief (acetaminophen). Subject will also document the date and time of membrane rupture if applicable.

Reasons for examining or removing dilators earlier include but are not limited to:

- 1) Spontaneous onset of labor  
(defined as regular, firm, uterine contractions with an effaced cervix >80% and a cervical dilatation > 3 cm)
- 2) Other than category I fetal heart rate tracing  
(category I includes all: Baseline rate: 110–160 beats per minute, baseline FHR variability: moderate, absent late or variable decelerations, Early decelerations: present or absent and accelerations: present or absent)
- 3) Spontaneous rupture of membranes or need for amniotomy
- 4) Spontaneous expulsion of Dilapan-S® rods
- 5) Subject removed the rods herself

After the designated 12 hours' time or earlier, if indicated, subjects are to return and to be admitted to L&D unit for standard protocol of labor induction. If the cervix remains unfavorable after extraction or spontaneous expulsion of the dilators (< 3cm and at most 60% effaced), additional mechanical or pharmacological cervical ripening may be provided at the provider's discretion. The agent/type will be recorded into the data sheet.

If subject does not return in the designated time and date as instructed (12 hours window), all attempts will be made to contact the subject by phone or supporting contact person. Subject will also be instructed that if she presents to another hospital, she needs to inform the clinical staff seeing her that she is participating in a trial and that Dilapan-S® was placed for cervical ripening, and to present the study card. We will also do our best to obtain our primary outcome through release of records.

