### **5.3. Randomization**

After Dilapan-S® placement, and if the subject remains eligible, subject will be randomized to the outpatient group or the inpatient group. A confidential computer-generated simple randomization scheme will be prepared and provided by independent vendor (PharmTest, s.r.o., Czech Republic) to our study coordinator. The currently used randomization code will be replaced by 2 randomization codes, 1 of them for CUMC site (both clinics will use the same randomization sequence. The randomization envelopes to be used at CUMC will be provided by UTMB).

A randomization log with group assignment, subject name, and medical record *number* will be used to track the randomization process. The subject will be included in the analysis by intent-to-treat once the randomization assignment has been made.

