### **VISIT #2**

#### **5.5. Labor Induction and Labor**

Management of the subject after the initial 12 hours of pre-induction or following the earlier removal or spontaneous expulsion of the dilator will be the same for both groups and at the discretion of the clinical team. Additional ripening (mechanical or prostaglandins) and/or oxytocin may or may not be needed. If needed, duration, type and dose of additional ripening agents and oxytocin will be documented.

Routine intrapartum care will be provided and relevant data collected by the subject's managing obstetrical team.

Trained and experienced research staff will be responsible for all research data abstraction. The PI and collaborators will review and validate the outcomes. If there is uncertainty, a second investigator will review the chart, discuss with the other investigators as needed, and make a final determination regarding the outcome.

Subjective assessment data will be collected, using adequate validated tools either after Dilapan-S® extraction or any time prior labor or post-partum (Appendix 3) at the time point best suitable for both the subject and the study team.

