### **6.2. Secondary Outcomes**

- Rate of vaginal deliveries (%)
- Rate of vaginal deliveries within 24 hours since admission to hospital (%)
- Rate of vaginal deliveries within 36 hours since admission to hospital (%)
- Time from hospital admission to reach active stage of labor defined as  $\geq 6$  cm (mins)
- Time from device placement to reach active stage of labor defined as  $\geq 6$  cm (mins)

- Change in Bishop score from insertion to extraction of device
- Change in cervical dilation after Dilapan-S®
- Rate of spontaneous vaginal deliveries after one round of cervical ripening (%) (no additional medical or mechanical interventions)
- Rate of operative vaginal deliveries (%)
- Rate of caesarean deliveries (%)
- Rate of artificial rupture of membranes (AROM) (%)
- Rate of epidural analgesia (%)
- Total duration of Dilapan-S® application (insertion to removal/extraction) (mins)
- Device placement to delivery interval (mins)
- Induction (Oxytocin/Prostaglandin initiation) to delivery interval (mins)
- Analgesia used during device placement (%), cervical ripening (%) and labor induction (%)
- Rate of adverse neonatal outcomes (composite and individual) –Apgar score <7 at 1-5-10 minutes, Cord arterial pH <7.1, neonatal ICU admission (%)
- Occurrence of maternal and neonatal complications within 2 weeks after delivery (%)
- Total duration of maternal hospital stay (hours)
- Subject reported clinical outcomes (sleep, rest, pain, activities of daily living, etc.) (Appendix 3)
- Subject reported satisfaction with Dilapan-S® treatment (Appendix 3)
- Medicaid charges for each hospitalized subject in both arms

*(Blood Bank Transfusion Operations, Chemistry Division, Hematopathology Division, JSH Labor & Delivery unit, Materials Management, Microbiology Division, Mother Baby Unit, Pharmacy, Respiratory Care Services, Surgical Operating Suite)*

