### **13.3. Analysis of secondary outcomes**

Nominal variables will be evaluated in the same manner as the primary outcome. Continuous variables will be summarized (minimum, maximum, mean, standard deviation, median, lower and upper quartile) and the difference between groups will be tested by t-test or Wilcoxon-Mann-Whitney test as appropriate. For time-to-event outcomes, Kaplan-Meier will be used to estimate the survival curves and log-rank test will be used to test the difference between groups by ITT analysis.

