## **Appendix 3:**

HOMECARE Protocol # 18-0132

Subject ID: HC -

Please think about the care you are receiving and circle the number which best indicates your agreement or disagreement with each of the following statements.

Please mark the pain level you've been experiencing during insertion of Dilapan-S.

A horizontal scale from 0 to 10 with the following labels: NO PAIN, MILD PAIN, MODERATE PAIN, SEVERE PAIN, and WORST PAIN POSSIBLE. Below the scale are seven smiley faces: a green smiley face at 0, a yellow smiley face at 1, an orange neutral face at 2, an orange frowny face at 3, an orange frowny face at 4, a red frowny face at 5, and a red sad face at 6.

Date:   -    
 Time:   :    
 Verified by:    
 (initials)

I am pleased with my overall cervical ripening experience with Dilapan-S.

*(this is process when your cervix becomes soften and distended by the device inserted)*

Strongly disagree Strongly agree  
 1  2  3  4  5

During the cervical ripening process, I was able to sleep and to rest.

Strongly disagree Strongly agree  
 1  2  3  4  5

During the cervical ripening process, I was able to walk, eat and shower.

Strongly disagree Strongly agree  
 1  2  3  4  5

Having my cervix soften and distended in a non-hospital environment  
 (not in the hospital) is beneficial and a great idea.

Strongly disagree Strongly agree  
 1  2  3  4  5

I would choose to have my cervix soften and distended in the hospital (not at home)  
 for my next pregnancy.

Strongly disagree Strongly agree  
 1  2  3  4  5

Please mark the pain level you've been experiencing while Dilapan-S was in place.

A horizontal scale from 0 to 10 with the following labels: NO PAIN, MILD PAIN, MODERATE PAIN, SEVERE PAIN, and WORST PAIN POSSIBLE. Below the scale are seven smiley faces: a green smiley face at 0, a yellow smiley face at 1, an orange neutral face at 2, an orange frowny face at 3, an orange frowny face at 4, a red frowny face at 5, and a red sad face at 6.

Date:   -    
 Time:   :    
 Verified by:    
 (initials)

*Thank you very much for taking your time to complete this questionnaire.*

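### Insertion pain is settled before randomisation but recorded after it in an open trial, so the rating is exposed to avoidable reporting bias

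*Combined protocol and SAP*

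**What the plan says.** Section 5.3 gives the order of events: "After Dilapan-S® placement, and if the subject remains eligible, subject will be randomized to the outpatient group or the inpatient group". Section 5.4.1 adds the interval between the two steps: "After Dilapan-S® placement, subject will be monitored for at least 30 minutes". Section 5.1 likewise places an observation period of 30 minutes before randomisation.

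Section 5.4.1 then times the pain rating: "After randomization subject will record the pain she experienced during insertion". The rating is made on the Appendix 3 survey, whose first pain item reads "Please mark the pain level you've been experiencing during insertion of Dilapan-S". It uses a 0 to 10 scale and has its own date, time and verification fields. A second, separate item asks about pain while the device was in place.

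Section 5.5, under Visit #2, gives a different timing for the subjective assessments as a whole: "either after Dilapan-S® extraction or any time prior labor or post-partum (Appendix 3".

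Section 6.2 lists among the secondary outcomes "Subject reported clinical outcomes (sleep, rest, pain, activities of daily living, etc", with a reference to Appendix 3, and does not separate the two pain items. For continuous secondary variables, section 13.3 states that "the difference between groups will be tested by t-test or Wilcoxon-Mann-Whitney test as appropriate". Section 13 leaves the detailed analysis to a SAP to be written before database lock.

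**The concern.** Insertion pain is in substance a pre-randomisation measurement. Recorded before allocation, it would be protected by randomisation: any difference between arms would be chance, and a 5% test would be positive 5% of the time. Recorded afterwards by a woman who knows whether she is leaving or being admitted, it loses that protection. Relief or disappointment about the assigned setting may change the rating she gives. If the item is left until after extraction or delivery, the ripening period itself may also colour her recall, and that period differs by arm.

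What is at stake is the interpretation of one patient-reported item. If it is tested along with the other secondary outcomes, a significant result would reflect chance or reporting, yet could be presented as an effect of setting. The documents give no reason for waiting until after randomisation.

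**Working it through.** **Order of events.** Putting sections 5.1, 5.3, 5.4.1 and 5.5 side by side gives:

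1. Dilators placed; insertion pain occurs.
2. Observation of at least 30 minutes.
3. Randomisation.
4. Insertion pain recorded (section 5.4.1), or, on one reading of section 5.5, recorded after extraction or post-partum.

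Step 1 precedes step 3, so the true expected difference between arms is zero. Step 4 follows step 3. The text says after randomisation, not after being told, so knowledge of the arm is an inference. It is a strong one: the documents describe no blinding, and the woman's next step is either home or a hotel, or admission.

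**Inputs.** The number per arm comes from section 13.4: 169, or 188 after allowance for dropout. That figure was checked first, using the pooled-variance formula for two proportions, 0.54 against 0.378, two-sided 5%, 85% power:

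- mean proportion = (0.54 + 0.378)/2 = 0.459
- n = [1.960 × √(2 × 0.459 × 0.541) + 1.036 × √(0.54 × 0.46 + 0.378 × 0.622)]² / 0.162² = 168.4, rounded up to 169
- 169/(1 − 0.10) = 187.8, rounded up to 188

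Both stated figures reproduce. This point does not depend on them except as the size of the comparison.

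The documents give neither an SD for the pain item nor any reporting shift. **Both are assumptions here:** SD 2, 2.5 or 3 points; shift between arms 0, 0.25 or 0.5 points.

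**Formula.** With b the shift and SE = SD × √(2/n), the chance of a two-sided 5% rejection (normal approximation) is Φ(b/SE − 1.96) + Φ(−b/SE − 1.96).

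Worked case, SD 2.5 and n = 169: SE = 2.5 × √(2/169) = 0.272.

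- b = 0.25: b/SE = 0.919; Φ(−1.041) + Φ(−2.879) = 15.1%.
- b = 0.5: b/SE = 1.838; Φ(−0.122) + Φ(−3.798) = 45.2%.

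| Assumed SD | n per arm | SE | No shift | Shift 0.25 | Shift 0.5 |
|---|---|---|---|---|---|
| 2 | 169 | 0.218 | 5% | 21.0% | 63.2% |
| 2 | 188 | 0.206 | 5% | 22.8% | 67.9% |
| 2.5 | 169 | 0.272 | 5% | 15.1% | 45.2% |
| 2.5 | 188 | 0.258 | 5% | 16.3% | 49.2% |
| 3 | 169 | 0.326 | 5% | 11.9% | 33.5% |
| 3 | 188 | 0.309 | 5% | 12.7% | 36.6% |

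The range is about 12–23% for a shift of 0.25 and 33–68% for 0.5. This shows how sensitive the comparison is to a small shift. It is not evidence that a shift occurs.

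**The case against.** The strongest reply is that little depends on this. It concerns one item of one secondary outcome. Because allocation cannot cause insertion pain, a careful reader would recognise an imbalance as chance or reporting. Nothing in the documents shows that any shift exists, and the figures above rest on assumed inputs. All of this stands, and it limits the weight of the point. It does not justify collecting the item after allocation when a suitable period exists before it.

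Three stronger readings are tempting but not supported.

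- A reader might infer that the two arms are asked at different times, because the instruction stands under the outpatient heading. The opening of section 5.4.1 describes steps common to all women, and the text narrows to the outpatient arm only after the pain sentence. Section 5.4.2 gives no other timing for inpatients. This is a matter of where the sentence sits, not evidence of unequal collection.
- A reader might infer that the plan commits to testing insertion pain between arms. Section 6.2 names pain only in general terms, next to sleep, rest and daily activities, and section 13 defers the detail to the SAP. A test is likely under section 13.3 but is not stated.
- A reader might infer that a planned baseline adjustment is spoiled. No analysis in the documents uses insertion pain as a baseline or covariate.

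Section 5.5 also need not contradict section 5.4.1 outright: its allowance for any time before labour could cover a rating made soon after randomisation. But it does not exempt the insertion item from the later times, so the two sections leave the timing open.

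**Conclusion.** The point holds as a minor, avoidable weakness. That the rating follows randomisation is explicit in section 5.4.1. That the woman then knows her arm is a strong inference in an open trial. That the item may be compared between arms follows from sections 6.2 and 13.3 read together, without being stated.

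The size of any bias cannot be established from the documents, and its direction is unknown. The calculated ranges hold only under the assumed SD and shift. The primary outcome and the sample size are unaffected.

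**What to change.** - **Section 5.4.1:** have every woman, in both arms, complete and time-stamp the insertion pain item during the observation of at least 30 minutes, before randomisation. The form already has the fields. Placing the instruction ahead of the arm-specific subsections would remove the ambiguity about whom it covers.
- **Section 5.5:** state that its later timing applies only to the other Appendix 3 items.
- **SAP:** report insertion pain descriptively as a pre-randomisation characteristic, not as a between-arm outcome. For women already enrolled, note that it was recorded after allocation. Using it as a covariate for pain while the rods are in place is optional.

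The cost is small but not nil. The form, the visit and the sample size stay the same, but the protocol needs an amendment. Section 5.3 speaks of a randomisation code in current use being replaced, which suggests that enrolment had begun; the data would then contain two collection times, which the recorded dates and times should separate. If few women remain to be enrolled, the SAP change does most of the work.

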#### **5.4.2. Group Assigned to Inpatient Cervical Ripening**

Subjects randomized to inpatient management will be admitted to L&D unit and standard clinical protocol will be initiated for cervical ripening and labor induction. During the period of 12 hours of cervical ripening subject is to remain "nothing per vagina" and undergo continuous fetal heart rate monitoring. During this period, clinical care will be left to the provider's discretion (standard of care at the institution) including "nil per os" or "nothing per os" (NPO) status. No other interventions are to occur during this period of 12 hours, unless clinically indicated. Reasons to remove the dilators and management after 12 hours will be the same as for the outpatient group (see sec. 4.4.1.).

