**Randomization** will be performed using a computer-generated random list of numbers assigning subjects to the 2 groups of the study. This list of random number assignments will be kept secure in an opaque envelope until the end of the study. 2 randomization sequences will be required for UTMB and CUMC sites.

No significant adverse effects are expected with the use of Dilapan-S® for mechanical dilation as an outpatient when compared to inpatient setting. The most common adverse events from cervical ripening with mechanical dilators such as the Foley balloon have been reported to be less than 1% (8), the most common being pain (0.26%), unintended amniotomy (0.04%), vaginal bleeding (0.07%), non-reassuring fetal heart tracing (0.07%), and uterine tachysystole (too low to quantify). Our group also reported the following adverse effects with inpatient use of Dilapan-S® for cervical ripening in a group of 444 subjects (9):

Maternal and neonatal adverse events	Nr. of cases (%)	Comments (n)
Uterine tachysystole	1 (0.2)	
Non reassuring fetal heart rate	1 (0.2)	
Maternal complications/discomfort	15 (3.4)	Bleeding during insertion/extraction of dilators (12), Cramping/pain (1), Other (1)
Uterine contractions	111 (25)	Tocography during cervical ripening showed low frequency and mild intensity contractions
Maternal infection	14 (3.2)	Chorioamnionitis (9), Urinary tract infection (3), Endomyometritis (1), Wound infection (1)

NICU admission	6 (1.4)	Meconium aspiration (2), Growth restriction (2), Asphyxia (1), Congenital cardiac abnormality (1)
Neonatal infection	1 (0.2)	Neonatal sepsis (maternal group B Streptococcus was not observed prior IOL)

The most significant potential risks noted with Dilapan-S® occur during or shortly after insertion and include vaginal bleeding due to cervical trauma and incidental rupture of membranes, as well as pain or discomfort with placement. If these occur and are persistent (i.e. unresolved pain despite analgesia), subjects will be admitted for delivery (as they require maternal monitoring) and will not be randomized, since they do not fulfill the eligibility criteria to receive the outpatient intervention.

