#### Definitions

**Adverse Event (AE)** is any untoward medical occurrence in a subject and that does not necessarily have a causal relationship to the study device and surgical procedure.

**Serious Adverse Event (SAE)** is any AE that:

- Results in death.
- Is life-threatening.
- Leads to hospitalization or prolongation of hospitalization.
- Causes disability and/or permanent impairment of a body function or structure.

- Requires medical or surgical intervention to prevent permanent impairment of a body function or permanent damage to a body structure.
- Leads to fetal demise, a congenital abnormality, or birth defect.

**Product Problem** includes:

- Inadequacy of a medical device with respect to its identity, quality, durability, reliability, safety or performance. It also includes inadequate labelling.
- Malfunction: failure of an investigational medical device to perform in accordance with its intended purpose when used in accordance with the instructions for use or Clinical Investigation Plan.
- User error: act or omission of an act that results in a different medical device response than intended by the manufacturer or expected by the user.

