#### *Safety Population*

The Safety population will be comprised of all subjects who had Dilapan-S® inserted and were randomized. This population will be used for the analysis of safety of the outpatient versus inpatient management. Subjects who were consented and had Dilapan-S® inserted, but not randomized, and had complications attributed to the device will be reported as AEs (detailed in section 9.1).

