**Appendix 4:**  
Safety Report Form

Research Protocol # 18-0132		Safety Report Form	

Forward completed information to:          MEDICEM Technology, [name]          e-mail: [contact]      [contact]
			
A. REPORTER (Physician, Nurse, Hospital, Other)			
1. Date of this Report: (dd-mmm-yyyy) - - - - -	2. Name:		
3. Address:			
4. Contact e-mail:	5. Contact Phone:		
B. PATIENT INFORMATION			
1. Subject ID: ..... or  Not Applicable	2. Year of Birth: (yyy) - - - -		
C. ADVERSE EVENT or PRODUCT PROBLEM			
1.  Adverse Event and/or  Product Problem (Device Deficiency)			
2. Outcome Attributed to Adverse Event (Check all that apply)  Death, incl. date: - - - - - (dd-mmm-yyyy)  Life-Threatening  Disability or Permanent Damage  Hospitalization (initial or prolonged)  Congenital Anomaly/Birth Defects  Required Intervention to Prevent Permanent Impairment/Damage			
3. Date of Event Onset: (dd-mmm-yyyy) - - - - -	4. This Report is:  Initial  Follow-Up		
5. Event or Problem Description (Narrative):     			
6. Other Relevant History, incl. Pre-existing Medical Conditions:   			
7. The Event or Problem Occurred:  Before Application  During Application  After Application			
8. Relationship to the Used Device: (only one option to be ticked)  Related (probably or possibly)  Not Related  Not possible to determine			
D. SUSPECTED MEDICAL DEVICE			
1. Product Name:	2. Lot #:		
3. Date of Expiration: (dd-mmm-yyyy) - - - - -	4. Date of Use: (dd-mmm-yyyy) - - - - -		
5. The Suspected Medical Device is being returned:  YES  NO			
DO NOT COMPLETE!			
E. SAFETY REPORT FORM RECEIPT (to be completed by Sponsor only)			
1. Date of Receipt: (dd-mmm-yyyy) - - - - -	2. Name:		
3. E-mail:	4. Phone:		
5. Report Reference:

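### Adverse events during the 12-hour ripening window are ascertained differently in the two arms, and the planned safety comparison neither separates tracing-detected events nor says how admission counts as serious

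*Combined protocol and SAP*

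**What the plan says.** Inpatients (section 5.4.2) are to "undergo continuous fetal heart rate monitoring" during the 12-hour ripening period. For outpatients, section 5.4.1 says "After Dilapan-S® placement, subject will be monitored for at least 30 minutes"; this observation comes before randomization. They then go home or, at one site, may use a hotel. "Subjects will also be instructed to return to L&D unit 12 hours after insertion, or earlier if any excessive bleeding", and the list continues with membrane rupture, pain, contractions and decreased fetal movement. The leaflet has space for pain medication, and the woman notes the time of any membrane rupture. No adverse event diary or standard query on return is described.

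One reason to examine or remove dilators is "Other than category I fetal heart rate tracing". Section 5.4.2 applies the same reasons to inpatients.

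Section 3 lists adverse events among the outcomes to be compared, and its data list covers complications during ripening and fetal decelerations. Of the Safety population, section 13.1 says: "This population will be used for the analysis of safety of the outpatient versus inpatient management". Section 13.3 tests nominal secondary outcomes in the same way as the primary, that is, by chi-square.

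One criterion for a serious adverse event (section 10.1, Definitions) is "Leads to hospitalization or prolongation of hospitalization". The form in Appendix 4 likewise covers initial and prolonged stays. Section 5.4.1 has every outpatient admitted for induction at 12 hours, or sooner if indicated.

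**The concern.** The trial hopes to show a shorter stay with no effect on maternal and neonatal outcomes (section 12). If events that mainly a monitor would reveal are counted in both arms and compared, a lower outpatient count may reflect only that nobody was recording. Such a result would look like evidence of safety.

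The seriousness criterion can work the other way. A woman at home who comes in early because of an event could have it coded as leading to hospitalization. The same event in a woman already admitted would be serious on this criterion only if it prolonged her stay. The documents do not say how an early return should be coded, given that admission was planned anyway.

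**Working it through.** **1. Inputs.** Section 13.4 gives 188 per arm. The figure reproduces from its own assumptions (0.54 versus 0.378, mean 0.459, two-sided 5%, power 85%):

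n = [1.960·√(2·0.459·0.541) + 1.036·√(0.54·0.46 + 0.378·0.622)]² / 0.162² = (1.381 + 0.721)² / 0.02624 ≈ 168.4, so 169 per arm. Then 169/0.9 = 187.8, so 188 per arm and 376 in total.

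This sizes the primary outcome. The documents give no power figure for safety.

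Event rates come from the inpatient registry table in section 3 (444 women): uterine contractions 111 (25%), with the comment "Tocography during cervical ripening showed low frequency and mild intensity contractions"; tachysystole 1 (0.2%); non-reassuring fetal heart rate 1 (0.2%).

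**2. Detection.** Assume equal true rates p, full detection in inpatients and a fraction s detected in outpatients. The values of s are assumed; the documents give none. The observed risk ratio is then s. With p₂ = s·p and p̄ the mean of p and p₂, the chance of a significant result showing fewer outpatient events is approximately

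Φ{ [(p − p₂)·√188 − 1.960·√(2·p̄·(1 − p̄))] / √[p(1 − p) + p₂(1 − p₂)] }.

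For p = 0.25 and s = 0.5: (0.125·13.711 − 1.960·0.552)/0.545 = 1.16, and Φ = 0.88. With s = 1 this one-directional chance is 2.5%.

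| True rate | s | Expected events, inpatient vs outpatient | Chance of a false difference |
|---|---|---|---|
| 25% (registry contractions) | 0.90 | 47.0 vs 42.3 | 8% |
| 25% | 0.75 | 47.0 vs 35.3 | 31% |
| 25% | 0.50 | 47.0 vs 23.5 | 88% |
| 10% (assumed) | 0.50 | 18.8 vs 9.4 | 45% |
| 5% (assumed) | 0.50 | 9.4 vs 4.7 | 25% |

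For tachysystole or non-reassuring heart rate, 188 × 1/444 ≈ 0.4 events are expected per arm. Even with no detection at home, no test would show a difference.

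**3. Seriousness.** Take an extreme case: a fraction q of outpatients (assumed) is admitted early for an event, each is coded serious for that reason alone, and no inpatient event is. Expected counts are 188 × 0.02 = 3.8 or 188 × 0.05 = 9.4, against 0. The two-sided Fisher p-value for k versus 0 is 2·C(188,k)/C(376,k). For k = 4 it is 2 × 0.0615 = 0.12; for k = 9 it is 2 × 0.0018 ≈ 0.004.

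**4. Where the difference stops.** Section 5.5 makes management after ripening the same in both arms. Sections 5.6, 5.7 and 6.2 collect delivery, neonatal and two-week outcomes with no stated difference by arm.

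**The case against.** Unequal observation is inherent in comparing home with hospital. Section 6.2 lists no tracing-detected ripening event and no serious adverse event rate: its safety items are the neonatal outcomes and the two-week complications, which are collected alike. Section 13 leaves detail to a SAP to be written before database lock. Section 10.1 limits reporting to the sponsor to events that are device-related or in doubt. The 25% row is the most frequent in the table and concerns mild contractions; section 9.3 lists tachysystole as a risk, not contractions as such. Section 5.4.2 names fetal heart rate only, so counting contractions assumes that tocography runs alongside.

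Much of this stands, and it narrows the point. It does not remove it: adverse events are still named for comparison in sections 3 and 13.1, ripening complications and decelerations are still collected, and the cited registry table itself counts contractions as adverse events.

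Three stronger readings are tempting and unsupported:

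- **That these events can be seen in one arm only.** Outpatients are told to return for contractions and other symptoms. Detection is less complete, not absent.
- **That the hospitalization criterion is one mainly outpatients can meet.** Inpatients can meet it through prolongation, and postpartum readmission is open to both arms. Only the initial limb during ripening is specific to outpatients, and its coding is undefined.
- **That the whole adverse event comparison is biased, or biased towards outpatient care.** The problem is confined to the ripening window, and the two mechanisms oppose each other.

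**Conclusion.** The point holds in limited form. Ascertainment differs by arm during ripening, and the plan neither separates the affected events nor says how a planned or early admission counts towards seriousness. Followed as written, it can produce a difference that is only an artefact of detection or coding.

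The size cannot be derived from the documents. In the illustrations it runs from under one event per arm at the registry's 0.2% rates to an 88% chance of a false difference for a 25% event half detected at home. That upper figure rests on equal true rates, an assumed detection fraction, tocography in inpatients, and contractions being counted and tested. The seriousness figures are an extreme case. The normal approximation is rough at low counts.

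The primary outcome and its sample size are unaffected. This is a cheap improvement.

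**What to change.** Add three rules to the SAP:

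1. Report tracing-detected ripening events (decelerations, tachysystole, contractions seen on tocography) descriptively by arm, without a test, and do not cite them as evidence of equal or better outpatient safety.
2. Keep ripening events that a woman can recognise herself (bleeding, membrane rupture, pain, expulsion) in the comparison from randomization in both arms, together with intrapartum, neonatal and two-week outcomes. Counting from hospital admission would not serve: inpatients are admitted at randomization and outpatients up to about 12 hours after insertion, and the period in which the arms differ would drop out.
3. For the arm comparison only, do not class an event as serious solely because of the planned induction admission or an early return for it. Apply the other seriousness criteria alike in both arms.

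The cost is SAP wording and fewer formally tested events. Safety reporting to the sponsor, monitoring and clinical care stay as they are.
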